## 9.3.3. Secondary Endpoints Analysis

## 9.3.3.1. Multiplicity Adjusted Endpoints

A graphical approach will be used to control the overall type I error for the primary objective and testing the superiority of LY3209590 compared with insulin degludec for

- 1) change from baseline in HbA1c at Week 26 (Visit 22)
- 2) the event rate of nocturnal hypoglycemia (<54 mg/dL [3.0 mmol/L] or severe) during treatment period up to Week 78 (Visit 37), and
- 3) time in glucose range between 70 and 180 mg/dL (3.9 and 10.0 mmol/L) inclusive collected during the CGM session prior to Week 26 (Visit 22).

The superiority test in change from baseline to Week 26 (Visit 22) in HbA1c will be based on the same primary endpoint analysis described above.

The rate of nocturnal hypoglycemia will be analyzed by a negative binomial regression with treatment, baseline HbA1c, baseline incidence of nocturnal hypoglycemia as independent variables, and log (exposure in year) as the offset.

The time in glucose range between 70 and 180 mg/dL (3.9 and 10.0 mmol/L) inclusive measured by CGM will be analyzed using an ANCOVA model for treatment regimen estimand and an MMRM model for efficacy estimand. In the ANCOVA model, treatment, strata (country, baseline HbA1c stratum [<8.0%,  $\geq 8.0\%$ ], and the type of basal insulin at randomization), and baseline of the dependent variable will be used. The MMRM model will include treatment, strata (country, baseline HbA1c stratum [<8.0%,  $\geq 8.0\%$ ], and the type of basal insulin at randomization), visit and treatment-by-visit interaction as fixed effects, and baseline of the dependent variable as a covariate. For treatment regimen estimand, the missing data will be imputed by multiple imputation with the approach similar to the imputation used for the primary endpoint.

## 9.3.3.2. Other Secondary Endpoints

Other secondary endpoints include various measures for efficacy, safety, and patient-reported outcome questionnaires. Efficacy measures and patient-reported questionnaires will be analyzed using the EAS2, unless otherwise noted. Safety measures will be analyzed using the SS regardless of treatment discontinuation and use of rescue medications.

Analysis details will be provided in the SAP.

## 9.3.4. Tertiary Endpoint(s) Analysis

Refer to the SAP for analyses related to tertiary endpoints.

## 9.3.5. Safety Analyses

Safety measures include treatment exposure, AE, vital signs, weight, hypoglycemia, laboratory measures and immunogenicity. All safety analyses will be based on the SS.

Events that are newly reported after the first dose of IP or reported to worsen in severity from baseline will be considered TEAEs. The Medical Dictionary for Regulatory Activities (MedDRA) lowest level term (LLT) will be used in the treatment-emergent assessment. The maximum severity for each LLT during the baseline period will be used as baseline severity.

TEAEs will be summarized in tables using the Medical MedDRA preferred term (PT), sorted by decreasing frequency within the LY3209590 treatment group for all TEAEs, TEAEs by maximum severity and common TEAEs (defined as ≥1% before rounding for LY3209590-treated participants). TEAEs will also be summarized by PT sorted by decreasing frequency within System Organ Class (SOC). For events that are specific to one sex, the denominator and computation of the percentage will include only participants from the given sex.

The number and percentage of participants who reported a serious AE (SAE) will be summarized by treatment group using MedDRA PT. A listing of all SAEs will also be provided.

The AEs leading to study treatment discontinuation will be summarized by treatment group using MedDRA PT. A listing of AEs leading to study treatment discontinuation will also be provided.

The participant-reported hypoglycemia: Level 1 (defined by glucose value  $\geq$ 54 to <70 mg/dL [ $\geq$ 3.0 to <3.9 mmol/L]), Level 2 (defined by glucose <54 mg/dL [3.0 mmol/L]), Level 3 (severe hypoglycemia) and the composite of Level 2 and Level 3, will be analyzed using data from e-diary. The analysis periods of 0-6, 0-12, 0-26, 0-52, 0-78, 12-26, 26-52, 26-78 weeks of treatment will be considered. Episodes for the 24-hour period, the non-nocturnal period (defined by 6 AM to midnight), and nocturnal period (defined by midnight to 6 AM) will be used to define all documented hypoglycemia, non-nocturnal hypoglycemia, and nocturnal hypoglycemia respectively. The incidence and rate of hypoglycemia will be summarized by treatment and analysis period for different types of hypoglycemia.

For continuous safety variables (for example, laboratory measures, vital signs, and weight), MMRM or ANCOVA models will be used. For categorical safety variables (for example, AEs, incidence of hypoglycemia, treatment-emergent abnormal laboratory measurements), either Fisher's exact test or logistic regression will be used for treatment comparison.

Further details for assessing all safety measures will be described in the SAP.

## 9.3.6. Other Analyses

## 9.3.6.1. Pharmacokinetic and Pharmacodynamic Analyses

LY3209590 concentration data will be analyzed using a population PK approach via nonlinear mixed-effects modeling with the NONMEM software. The relationships between LY3209590 dose and/or concentration and efficacy, and safety as well as biomarker endpoints may be characterized. In addition, if population PK and PK/PD models can be established, the impact of additional participant factors, such as age, weight, gender, and renal function on PK and/or PD

parameters, may be examined. Should antidrug antibody be detected from immunogenicity testing, its impact on LY3209590 PK or any relevant PD parameters will also be examined.

## 9.3.6.2. Evaluation of Immunogenicity

The baseline anti-LY3209590-antibody (ADA) status (detected or not detected) will be summarized by treatment for the participants evaluable for treatment-emergent ADA (TEADA) defined as participants with non-missing baseline and at least one non-missing postbaseline measurement.

The number and percentage of participants who are treatment-emergent ADA positive  $(\underline{\text{TEADA}})$  will be summarized by treatment group. A participant who is evaluable for TEADA is TEADA+ if either of the following holds:

- treatment induced ADA: the participant has baseline status of ADA Not Present and at least 1 postbaseline status of ADA Present with titer ≥2-fold (1 dilution) of the minimum required dilution (1:20)
- treatment boosted ADA: the participant has baseline status of ADA Present and at least 1 postbaseline status of ADA Present with the titer being ≥2 dilutions (4-fold) of the baseline titer. That is, the participant has baseline status of ADA Present, with titer 1:B, and at least 1 postbaseline status of ADA Present, with titer 1:P and P/B≥4.

The frequency of cross-reactive binding to endogenous insulins may also be summarized for the participants with TE ADA+.

The relationship between the presence of TEADA and the safety and efficacy measures may be assessed.

# 9.4. Interim Analysis

A program level safety review using selected efficacy and safety data will be conducted on a periodic basis across all ongoing Phase 3 clinical trials evaluating LY3209590. The analysis will be performed using the unblinded data and be reviewed by the DMC consisting of experienced members external to Lilly. Study team personnel will remain blinded. Detailed information for the data review and the unblinding are specified in the DMC Charter or a separate unblinding plan document.

# 9.5. Sample Size Determination

Approximately 939 participants will be randomly assigned to LY3209590 and insulin degludec in a 2:1 ratio. With the assumption of 15% dropout at Week 26, approximately 532 and 266 participants will complete 26 weeks of treatment on LY3209590 and insulin degludec, respectively.

The primary objective of this study is to test the hypothesis that LY3209590 is noninferior to insulin degludec on glycemic control as measured by change from baseline to Week 26 (Visit 22) in HbA1c in participants with T2D currently on basal insulin.

Assuming a noninferiority margin (NIM) of 0.4%, no true difference between treatment groups, and a SD of 1.1%, 798 completers (532 on LY3209590 and 266 on insulin degludec) will provide greater than 99% statistical power to show noninferiority between LY3209590 and insulin degludec using the upper limit of a 2-sided 95% confidence interval (LY3209590 – insulin degludec). This sample size also has at least 95% statistical power to show noninferiority between LY3209590 and insulin degludec using a 0.3% NIM at Week 26.

The 798 completers will provide 95% statistical power to demonstrate the superiority (LY3209590 vs. insulin degludec) of change in HbA1c from baseline to 26 weeks (assuming a SD of 1.1% and true mean difference is -0.3%) using the alpha of 0.05.

The 798 completers will provide at least 95% statistical power to show the superiority of the percentage of time in glucose range between 70 and 180 mg/dL (3.9 and 10.0 mmol/L) inclusive during the CGM session prior to Week 26 between LY3209590 and insulin degludec (assuming a SD of 18% and true mean difference is 5%) at alpha = 0.05.

The 798 participants will provide at least 80% statistical power to show the superiority of the event rate of clinically significant nocturnal hypoglycemia (<54 mg/dL [3.0 mmol/L] or severe) during treatment phase up to Week 78 (assuming event rate of 0.67 [SD = 2.6] and 1.1 [SD = 2.6] events per participant per year for LY3209590 and insulin degludec, respectively) using a negative binomial distribution at alpha = 0.05.

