# 9.3. Statistical Analyses

## 9.3.1. General Considerations

Statistical analysis of this study will be the responsibility of Lilly or its designees. Any change to the data analysis methods described in the protocol will require an amendment ONLY if it changes a principal feature of the protocol. Any other changes to the data analysis methods described in the protocol, and the justification for making the change, will be described in the SAP or the clinical study report. Additional exploratory analyses of data will be conducted as deemed appropriate.

Unless otherwise stated, the efficacy analyses will be conducted on either EAS1 (for treatment regimen estimand) or EAS2 (for efficacy estimand) and the safety analyses will be conducted on SS. All tests of treatment effects using statistical models will be conducted at a 2-sided alpha level of 0.05 and 2-sided 95% CI will be provided. Unless otherwise specified, other secondary and tertiary efficacy measures will be analyzed using EAS2 with the data up to the discontinuation of study treatment (defined by the date of last study dose + 10 days) or the initiation of rescue medication whichever is earlier.

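### The printed inputs for nocturnal hypoglycemia give about 57–63% power with 798 participants, not the stated 80% or more

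*Protocol*

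**What the plan says.** Protocol 9.5 makes this claim: "The 798 participants will provide at least 80% statistical power to show the superiority of the event rate of clinically significant nocturnal hypoglycemia". The rates and SDs are given as "assuming event rate of 0.67 [SD = 2.6] and 1.1 [SD = 2.6] events per participant per year", for LY3209590 and insulin degludec in that order, and the calculation is described as "using a negative binomial distribution at alpha = 0.05". SAP Section 5 repeats the paragraph with the same figures.

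The 798 are the expected Week 26 completers: "approximately 532 and 266 participants will complete 26 weeks of treatment on LY3209590 and insulin degludec, respectively". The number randomized is larger: "Approximately 939 participants will be randomly assigned to LY3209590 and insulin degludec in a 2:1 ratio". Tests are two-sided (Protocol 9.3.1): "All tests of treatment effects using statistical models will be conducted at a 2-sided alpha level of 0.05". The planned analysis (Protocol 9.3.3.1) is a negative binomial regression with log exposure as offset: "The rate of nocturnal hypoglycemia will be analyzed by a negative binomial regression with treatment", plus baseline covariates.

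The observation window is given as the treatment phase up to Week 78. Dropout is given only to Week 26 (15%). No dispersion parameter, mean exposure or separate time scale for the SD is printed.

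**The concern.** For a negative binomial comparison, power is fixed by the two rates, the dispersion, the exposure and the arm sizes. A mean and an SD on a known time scale determine a dispersion. Here the SDs are attached to annual rates, so the natural reading is 2.6 events per year in each arm. On that reading the power comes out well below the stated figure.

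This endpoint is one of three superiority hypotheses in the multiplicity-controlled family. Protocol 9.1.1.1 says the alpha allocation will take the statistical power of the endpoints into account, so the figure is an input to the design. It also bears on how a non-significant result would be read.

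**Working it through.** **Inputs (Protocol 9.5, repeated in SAP Section 5).** Rates r1 = 0.67 (LY3209590) and r0 = 1.1 (degludec) per participant-year; SD 2.6 in each arm, so variance 6.76; n1 = 532, n0 = 266; two-sided alpha 0.05, critical value 1.96. The 78-week window is taken as 1.5 years.

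**The section's other power statements, as a check of method.** For 532/266, power = Φ(Δ / [SD·√(1/532 + 1/266)] − 1.96).

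| Statement | Δ | SD | Computed | Stated |
|---|---|---|---|---|
| Noninferiority, margin 0.4% | 0.4 | 1.1 | 99.8% | over 99% |
| Noninferiority, margin 0.3% | 0.3 | 1.1 | 95.3% | at least 95% |
| HbA1c superiority | 0.3 | 1.1 | 95.3% | 95% |
| Time in range | 5 | 18 | 95.9% | at least 95% |

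All four reproduce from their printed inputs.

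**The hypoglycemia statement, as printed.**

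- Effect: |ln(0.67/1.1)| = 0.4958.
- Dispersion, k = (SD² − mean)/mean²: (6.76 − 0.67)/0.4489 = 13.57 for LY3209590; (6.76 − 1.1)/1.21 = 4.68 for degludec.
- Variance of the log rate ratio: (1/(r1·t) + k1)/n1 + (1/(r0·t) + k0)/n0.
- t = 1 year: 6.76/(0.4489 × 532) + 6.76/(1.21 × 266) = 0.0283 + 0.0210 = 0.0493; SE 0.2221; power Φ(0.4958/0.2221 − 1.96) = 60.7%.
- t = 1.5 years: 0.0274 + 0.0199 = 0.0472; SE 0.2173; power 62.6%.
- Difference in means: 0.43/(2.6 × √(1/532 + 1/266)) = 0.43/0.1952 = 2.20; power 59.6%.
- Simulation of a common-dispersion negative binomial fit without covariates, two separate sets of runs: 56.5% and 57.3% (1 year); 57.4% and 58.9% (1.5 years).

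So the range is about 57–63%.

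**Variations that keep both printed SDs on the per-year scale.** All 939 (626/313): 67.8% (1 year), 69.7% (1.5 years). One-sided alpha 0.05 with 798, 1 year: 72%. None reaches 80%.

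**What 80% would need on this reading.** SE = 0.4958/(1.96 + 0.84) = 0.177. That means a common SD of about 2.07 (1 year) or 2.14 (1.5 years), or about 1,256 (1 year) or 1,204 (1.5 years) participants at 2:1.

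**Readings that depart from the printed text.**

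| Reading | 798 | 939 | Conflict with the text |
|---|---|---|---|
| k = 4.68 in both arms, 1.5 years | 81.0% | 86.8% | Implies LY3209590 SD √(0.67 + 4.68 × 0.4489) = 1.66, not 2.6 |
| k = 4.68 in both arms, 1 year | 78.4% | 84.6% | Same |
| k = 13.57 in both arms, 1.5 years | 41.5% | 47.4% | Degludec SD no longer 2.6 |
| 2.6 as SD of the 78-week count | 91.8% | 95.3% | Sets aside the per-year scale |

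For the last row the 78-week means are 1.005 and 1.65, k is 5.70 and 1.88, and with 798 the SE is 0.148.

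**The case against.** The strongest defense is that the planned regression estimates one dispersion for both arms, so unequal dispersions of 13.57 and 4.68 do not belong to that model. Taking the dispersion from the control arm over the 78-week window gives 81.0%, close to the claim. It stays above 80% for mean exposure of about 1.3 years or more. On this account the power is right and the second SD was simply carried over. That is plausible, and nothing in the documents excludes it. Nothing confirms it either, and it makes the printed LY3209590 SD wrong.

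Three further points have some force.

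- The hypoglycemia analysis uses all treated participants, so the analyzed number should be nearer 939 than 798. This raises power on every reading, but only to 68–70% on the printed one. The claim itself is made for 798.
- Adjustment for baseline HbA1c and hypoglycemia history may lower the residual dispersion. The documents give no figure for that gain, and the calculations here do not include it.
- The window to Week 78 is stated. What is missing is the mean exposure assumed within it and the dropout after Week 26.

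It is also fair that a planning figure for one key secondary endpoint does not affect the validity of the test.

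**Conclusion.** The power statement and its printed inputs do not agree. With an SD of 2.6 per year in both arms, 798 participants give about 57–63%, roughly 20 percentage points short. Either the power is overstated or one of the printed inputs is not the one used.

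This does not show that the endpoint is underpowered. Depending on what was actually assumed, the planned figure could have been about 60%, 81% or 92%. The calculations assume two-sided 0.05 at full alpha, equal follow-up for all participants and no covariate adjustment. If the graphical procedure gives this endpoint less than 0.05 at the step where it is tested, power there would be lower; that allocation was not available here and is not used. Type I error, the analysis model and the sample size for the primary objective are unaffected.

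**What to change.** Correct the paragraph in Protocol 9.5 and SAP Section 5 so that the rates, the SD or dispersion, the exposure and the power are consistent.

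- If 2.6 is the per-year SD in both arms, restate the power as about 60% for 798 participants, or just under 70% for 939.
- If a common dispersion was used, print it with its source and the mean exposure, and correct the LY3209590 SD.
- If 2.6 is the SD of the 78-week count, say so and give the matching power.

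In each case state the number analyzed and the dropout assumed after Week 26. The cost is one paragraph in each document, and the stated power may become less favorable. No change to the sample size or the analysis is needed.

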# **10.** Supporting Documentation and Operational Considerations

# 10.1. Appendix 1: Regulatory, Ethical, and Study Oversight Considerations

## **10.1.1.** Regulatory and Ethical Considerations

- This study will be conducted in accordance with the protocol and with the following:
  - consensus ethical principles derived from international guidelines including the Declaration of Helsinki and CIOMS International Ethical Guidelines
  - applicable ICH GCP Guidelines, and
  - applicable laws and regulations.
- The protocol, protocol amendments, ICF, IB, and other relevant documents (for example, advertisements) must be submitted to an IRB/IEC by the investigator and reviewed and approved by the IRB/IEC before the study is initiated.
- Any amendments to the protocol will require IRB/IEC approval before implementation of changes made to the study design, except for changes necessary to eliminate an immediate hazard to study participants.
- Protocols and any substantial amendments to the protocol will require health authority approval prior to initiation except for changes necessary to eliminate an immediate hazard to study participants.
- The investigator will be responsible for the following:
  - providing written summaries of the status of the study to the IRB/IEC annually or more frequently in accordance with the requirements, policies, and procedures established by the IRB/IEC
  - notifying the IRB/IEC of SAEs or other significant safety findings as required by IRB/IEC procedures, and
  - providing oversight of study conduct for participants under their responsibility and adherence to requirements of 21 Code of Federal Regulations (CFR), ICH guidelines, the IRB/IEC, European regulation 536/2014 for clinical studies (if applicable), and all other applicable local regulations.
- Investigator sites are compensated for participation in the study as detailed in the CTA.

## **10.1.2.** Financial Disclosure

Investigators and sub-investigators will provide the sponsor with sufficient, accurate financial information as requested to allow the sponsor to submit complete and accurate financial certification or disclosure statements to the appropriate regulatory authorities. Investigators are

responsible for providing information on financial interests during the course of the study and for 1 year after completion of the study.

#### 10.1.3. Informed Consent Process

- The investigator or the investigator's representative will explain the nature of the study, including the risks and benefits, to the participant or the participant's legally authorized representative and answer all questions regarding the study.
- Participants must be informed that their participation is voluntary. Participants or their legally authorized representatives will be required to sign a statement of informed consent that meets the requirements of 21 CFR 50, local regulations, ICH guidelines, privacy, and data protection requirements, where applicable, and the IRB/IEC or study center.
- The medical record must include a statement that written informed consent was obtained before the participant was entered in the study and the date the written consent was obtained. The authorized person obtaining the informed consent must also sign the ICF.
- Participants must be reconsented to the most current version of the ICF(s) during their participation in the study.
- A copy of the ICF(s) must be provided to the participant or the participant's legally authorized representative and is kept on file.

#### 10.1.4. Data Protection

- Participants will be assigned a unique identifier by the sponsor. Any participant records, datasets, or tissue samples that are transferred to the sponsor will contain the identifier only; participant names or any information which would make the participant identifiable will not be transferred.
- The participant must be informed that the participant's personal study-related data will be used by the sponsor in accordance with local data protection law. The level of disclosure must also be explained to the participant who will be required to give consent for their data to be used as described in the informed consent.
- The participant must be informed that their medical records may be examined by Clinical Quality Assurance auditors or other authorized personnel appointed by the sponsor, by appropriate IRB/IEC members, and by inspectors from regulatory authorities.
- The sponsor has processes in place to ensure data protection, information security, and data integrity. These processes include appropriate contingency plan(s) for appropriate and timely response in the event of a data security breach.

## **10.1.5.** Committees Structure

#### 10.1.5.1. Internal Safety Review Team

Participant safety will be continuously monitored by the sponsor's internal safety review team, which includes safety signal detection at any time during the study.

All safety data collected will be summarized and reviewed by the sponsor's internal safety review team for agreement of next steps.

#### 10.1.5.2. Clinical Event Committee for Adjudication of Cerebrocardiovascular Events

A blinded Clinical Event Committee, external to Lilly, will adjudicate cerebrocardiovascular events.

#### 10.1.5.3. Data Monitoring Committee

An independent external DMC will be responsible for reviewing unblinded data during the study.

The committee will include, at a minimum, a medical physician with appropriate expertise and a statistician.

Access to the unblinded data will be limited to the DMC and the external Statistical Analysis Center statisticians who are providing the analysis of the data. These statisticians will be independent from the study team. The study team will not have access to the unblinded data. Only the DMC is authorized to evaluate unblinded interim analyses.

Details about the membership, purpose, responsibilities, and operation will be included in the DMC charter.

An early PK/PD unblinded transfer may also be conducted. Only a small group of personnel may be unblinded to the data for the potential PK/PD analysis and must keep information confidential until the planned unblinding of the trial.

